 - Alternative hypothesis is that there is significant difference in the proportion of subjects who experience the occurrence of an episode of atrial fibrillation during the infusion protocol when comparing those who receive the isoprenaline infusion with those who receive the placebo infusion.
 - Double blinded. Event rate in Isoprenaline group likely <10%. Event rate in placebo group likely <5%. For 90% power and 95% significance projected to need 133 participants per group.
 - Descriptive data only, not feasible to power properly for this endpoint but may be reasonable to use a 1 sided test. Aim to recruit 35 participants per group.

Experiment 5

- Does a Cavo-tricuspid isthmus ablation for atrial flutter alter inducibility of atrial fibrillation using an isoprenaline infusion?
 - Null hypothesis under investigation is that the proportion of subjects in whom there is a change in the occurrence of atrial fibrillation between two administrations of an infusion of isoprenaline is not less than 20%. Where one administration is before and one is after an atrial flutter ablation procedure.
 - Alternative hypothesis is that the proportion of subjects in whom there is a change in the occurrence of atrial fibrillation between two administrations of an infusion of isoprenaline is less than 20%. Where one administration is before and one is after an atrial flutter ablation procedure.
 - Double blinded, placebo controlled. Event rate >30%
 - A 95%Cl of +/- 10% around an expected % disagreement of 10% would require 35 participants

Experiment 6

- Does an ablation procedure for a AVRT or AVNRT alter inducibility of atrial fibrillation using an isoprenaline infusion?
 - Null hypothesis under investigation is that the proportion of subjects in whom there is a change in the occurrence of atrial fibrillation between two administrations of an infusion of isoprenaline is not less than 20%. Where one administration is before and one is after an SVT ablation procedure.
 - Alternative hypothesis is that the proportion of subjects in whom there is a change in the occurrence of atrial fibrillation between two administrations of an infusion of isoprenaline is less than 20%. Where one administration is before and one is after an SVT ablation procedure.
 - Double blinded, placebo controlled. Event rate <10%
 - A 95%Cl of +/- 10% around an expected % disagreement of 10% would require 35 participants

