The Participant Information Sheet (PiS) will be specific to the part of the study a subject is being recruited to. The "Participant Information Sheet for those being recruited to the Cardiac Ward based Infusion Protocol" will be for those recruited to protocol Part A and includes subjects in group 1. The "Participant Information Sheet for those being recruited to the Cardiac Electrophysiology Laboratory Infusion Protocol" will be for those recruited to protocol Part B and includes those from groups 2, 3 and 4. The "Additional Information Sheet for those undergoing an ablation for Atrial Flutter or Atrial Fibrillation" will be given to participants recruited to groups 3 and 4.

Informed Consent

Informed consent to enter the study must be sought from each participant. This will be taken only after a full explanation has been given, an information leaflet offered and time allowed for consideration. Signed participant consent will be obtained. The right of the participant to refuse to participate without giving reasons will be respected.

Sample Size Calculation

The sample size calculation for estimation of the proportion of disagreement between repeated isoprenaline infusions in terms of ability to induce atrial fibrillation is based on the width of a 1-sided 95% confidence interval (CI). Assuming that the proportion of disagreement will be \leq 10%, a sample size of 35 patients would enable the proportion to be estimated with an upper limit of the 1-sided 95%CI for the proportion of \leq 20%.

A 1-sided CI is used as we only wish to ensure that the upper limit of the estimated proportion of disagreement is less than a given cut-off (20% has been chosen to indicate clinically significant disagreement); the lower limit of the CI is immaterial as the lower the proportion of disagreement the better, so we do not need to restrict this.

The sample size calculation for the randomised comparison of proportion of participants inducible in the placebo and isoprenaline arms is based on the chi-squared test. In the Pulmonary Vein Isolation Group, assuming that almost no participants in the placebo arm will be inducible (1%), and that the proportion of participants in the active drug (isoprenaline) arm who are inducible will be 30%, then 31 patients in each arm will be required for 90% power (assuming 2-sided significance of 5%).

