It is noted that previous literature suggests that the proportion of patients with a past history of atrial fibrillation who are inducible with isoprenaline is greater than 80%. This does not fit with our interpretation of day to day clinical practice and hence the study is powered to detect a far lower arte of inducibility. We will however perform a pre-specified interim analysis of the Pulmonary Vein Isolation Group once 10 participants with a past history of atrial fibrillation have been randomised to each arm of the study (Experiment 2). If a significant result is detected, enrolment to that block will be discontinued.

Statistical analysis

The analysis of the disagreement between repeated isoprenaline infusions in terms of ability to induce atrial fibrillation will estimate the proportion of disagreement with a 1-sided 95%CI for the proportion. A 2-sided 90%CI is first calculated and the upper limit of this interval gives the required upper limit of a 1-sided 95%CI. If the estimated upper limit is < 20% (the chosen cut-off for clinically significant disagreement) then agreement between repeated infusions will be considered acceptable.

The randomised comparison of proportion of patients inducible between placebo and isoprenaline will use the chi-squared test or the Fisher's exact test if numbers of patients in some categories are small.

It is anticipated that the rate of induced episodes of arrhythmia in a number of the groups where they are being given placebo infusion will approach zero. If the results of the study demonstrate that the rate of inducibility in the SVT group or atrial flutter group being given placebo infusion is zero, we would consider it acceptable to use one sided tests of significance.

Study Duration

We aim to recruit 235 participants over a 24 month recruitment period. It is anticipated that the majority of subjects will be recruited from the Bournemouth site.

- Start Date: 01/09/2014
- Estimated Date of End of Trial: 01/09/2017
- Maximum Duration of Participation: 12 months

Study Procedure

The study will require a minimum of 2 encounters with the study team. For subjects in the group of participants requiring the most visits, the study schedule requires 7 visits over 12 months. Usual care for this group would involve 4 visits to hospital, one of these is not required by the study participants and 3 are combined with study visits.

Infusion Protocol

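### One-sided testing in the SVT and atrial flutter groups is triggered by the observed placebo count, with no one-sided significance level stated

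*Protocol*

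**What the plan says.** The rule is in the protocol's Statistical analysis section. Its condition opens "If the results of the study demonstrate that the rate of inducibility in the SVT group or atrial flutter group" and ends "being given placebo infusion is zero, we would consider it acceptable to use one sided tests of significance". No significance level is attached to the one-sided test. The same section says that the randomised comparison "will use the chi-squared test or the Fisher's exact test if numbers of patients in some categories are small", without defining small.

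Three other places bear on it:

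- Study Objectives, Experiments 3 (flutter) and 4 (SVT): both set a null of no difference against an alternative of a difference, with no direction. Both give 90% power and 95% significance without naming the sidedness. They project 31 and 133 per group, and each aims to recruit 35 per group.
- Study Objectives, Experiment 4: the data are called descriptive only, "not feasible to power properly for this endpoint but may be reasonable to use a 1 sided test". The zero-placebo condition does not appear here.
- Sample Size Calculation: the one explicit statement of sidedness for the randomised comparison, "assuming 2-sided significance of 5" per cent, is made for the Pulmonary Vein Isolation Group.

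**The concern.** A one-sided test is defensible when direction and level are fixed before the data are seen. Here the trigger is a result. Once the placebo arm has no events, the observed difference cannot point towards placebo, so dropping the other tail gives up nothing and simply halves the p-value. The permissive wording adds a second choice made after the data are known, namely whether to use the option.

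The trigger is also likely to be met, because the same section expects placebo induction rates close to zero. At stake is whether Experiment 3, a formally powered comparison, could be called positive on a result that fails the two-sided test its hypotheses and sample size imply. The two places that mention one-sided testing also disagree on when it applies: the Statistical analysis section requires zero placebo events, and Experiment 4 requires nothing.

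**Working it through.** **Inputs.** 35 per group in Experiments 3 and 4 (Study Objectives); 1:1 allocation (Study Procedure, Protocol Part B); chi-squared or Fisher (Statistical analysis). Planning rates come from Sample Size Calculation: "assuming that almost no participants in the placebo arm will be inducible (1" per cent, and "the proportion of participants in the active drug (isoprenaline) arm who are inducible will be 30" per cent. Assumption: the one-sided test is run at 5%, since the protocol gives no level.

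**Step 1. The plan's own figures.** Per-arm size, pooled variance, no continuity correction:

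n = [z(1−α/2)·√(2p̄q̄) + z(1−β)·√(p₁q₁+p₂q₂)]² / (p₁−p₂)²

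- 1% v 30%, p̄=0.155: (1.960×0.5118 + 1.2816×0.4689)² / 0.29² = 1.604² / 0.0841 = 30.6, so 31. This matches "31 patients in each arm will be required for 90% power (assuming 2-sided significance of 5" per cent). One-sided 5% gives 25.
- 1% v 10%, p̄=0.055: (1.960×0.3224 + 1.2816×0.3161)² / 0.09² = 1.037² / 0.0081 = 132.8, so 133, the Experiment 4 figure. One-sided gives 109.

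Two-sided sizing for Experiments 3 and 4 is therefore an inference from this match, and it needs a 1% placebo rate. At the 5% bound those experiments quote, 5% v 30% needs 47 two-sided or 38 one-sided, and 5% v 10% needs 582 or 474. None of these gives 31 or 133.

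**Step 2. p-values with zero placebo events, 35 per arm.** Fisher one-sided: p = C(35,x)/C(70,x); the two-sided value is twice this because the arms are equal. Uncorrected chi-squared: χ² = 70x/(70−x).

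| Isoprenaline v placebo | Fisher two-sided / one-sided | Chi-squared two-sided / one-sided |
|---|---|---|
| 3 v 0 | 0.239 / 0.120 | 0.077 / 0.038 |
| 4 v 0 | 0.114 / 0.057 | 0.039 / 0.020 |
| 5 v 0 | 0.054 / 0.027 | 0.020 / 0.010 |
| 6 v 0 | 0.025 / 0.012 | 0.010 / 0.005 |

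Under Fisher only 5 v 0 changes verdict; under uncorrected chi-squared only 3 v 0 does. Continuity-corrected chi-squared behaves like Fisher (5 v 0: 0.063 to 0.032). At 31 per arm, Fisher 5 v 0 is 0.053 to 0.026, so the threshold is the same.

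**Step 3. How often the condition is met.** P(no placebo events) = (1−p)³⁵, which is 70% at a true rate of 1% and 17% at 5%.

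**Step 4. Type I error, both directions, by exact enumeration at a common 5% rate.** The rule adds the probability of the one table that changes.

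- Fisher: C(35,5)·0.05⁵·0.95³⁰ × 0.95³⁵ = 0.0218 × 0.166 = 0.0036, so 0.26% becomes 0.62%.
- Uncorrected chi-squared: C(35,3)·0.05³·0.95³² × 0.95³⁵ = 0.1585 × 0.166 = 0.0263, so 3.6% becomes 6.3%. The peak is 6.8% at a common rate of 7%, where the fixed rule gives 5.1%.
- Fisher only where an expected count is below 5 (an assumed reading of small): 0.27% becomes 0.63%.

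**Step 5. Chance that the pivotal Fisher table occurs.** At 30% v 1%: C(35,5)·0.3⁵·0.7³⁰ × 0.703 = 0.0178 × 0.703 = 1.3%, so power moves from 93.5% to 94.8%. At 10% v 1%: 0.1376 × 0.703 = 9.7%, so power moves from 9.8% to 19.5%.

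**The case against.** The best defence is that the practical effect is small. In tables this sparse (3 v 0 and 4 v 0 have expected counts of 1.5 and 2 per arm) the plan's own clause points to Fisher, which is so conservative here that the rule leaves total error far below 5%. One table changes verdict, and at Experiment 3's planning rates it would occur about 1% of the time. The expected direction was also declared beforehand: placebo rates below 5% and close to zero. The sentence permits one-sided tests without requiring them. All of this stands, and it limits the size of the point. It does not justify the rule, because a direction known in advance supports a one-sided test fixed in advance, not one that depends on the placebo count.

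Three stronger readings are tempting but not supported:

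- A reader might infer that type I error is pushed above 5%. That needs uncorrected chi-squared where the small-numbers clause points to Fisher.
- A reader might infer that the significance level is doubled outright. That holds for the nominal level in one direction and for the p-value, and only if the one-sided test is run at 5%. At 2.5% the problem disappears.
- A reader might infer a direct contradiction with the two-sided 5% in Sample Size Calculation. That sentence concerns the Pulmonary Vein Isolation Group, which the one-sided rule does not cover. The conflict is with the non-directional hypotheses of Experiments 3 and 4 and, by inference, with their sample sizes.

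**Conclusion.** The point holds. The protocol lets an observed outcome decide the sidedness of the test in the SVT and flutter groups and leaves the one-sided level unstated. If that level is 5%, the nominal error favouring isoprenaline goes from 2.5% to 5%, and one event fewer is enough for significance (five instead of six under Fisher at 35 per arm). A result with a planned two-sided p of 0.054 could then be reported as 0.027.

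The realised error under Fisher remains small, so the fault lies in the validity and meaning of the reported p-value more than in a large excess of false positives. It matters most for Experiment 3. The pivotal table is likelier in Experiment 4, at about 10%, but that experiment is labelled descriptive. The conclusion rests on 35 per arm, a one-sided level of 5%, and Fisher being used when counts are small.

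**What to change.** Delete the conditional one-sided sentence from Statistical analysis and the one-sided clause from Experiment 4. In their place, state that the SVT and atrial flutter comparisons are tested at two-sided 5%, or equivalently one-sided 2.5%, whatever the placebo count. Leave the chi-squared/Fisher choice and Experiment 2 as they are, since the one-sided rule does not touch them.

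The cost is two short edits and no extra participants, because 31 and 133 already reproduce as two-sided calculations. The price is a slightly lower chance of significance: under Fisher at 35 per arm, about 1 percentage point at 30% v 1% (Experiment 3) and about 10 points at 10% v 1% (Experiment 4, where power is at most 19.5% either way).

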Torbay Pharmaceuticals South Devon Healthcare NHS Foundation Trust [name]

[contact] 664707Fax01803 664354

Manufacturing Site:

Pharmaceutical Manufacturing Unit [name]

Investigational Medicinal Product (IMP)

Isoprenaline Sulphate

Isoprenaline is a synthetic, sympathomimetic amine that is structurally related to epinephrine but acts almost exclusively on beta-adrenergic receptors. It is a short acting, non-selective beta agonist with very low affinity for alpha adrenoceptors. The drug is produced in two forms, isoprenaline sulphate and isoprenaline hydrochloride. The hydrochloride form is more potent with 1mg of the hydrochloride equivalent to 1.125mg of the sulphate(1). The chemical formula for Isoprenaline Sulphate is $(C_{11}H_{17}NO_3)_2, H_2SO_4$. It has a relative molecular mass of 556.6. Synonyms include Isoproterenol and Bis[(1RS)·1·(3,4·dihydroxyphenyl)·2·[(1·methylethyl)·amino]ethanol] sulphate dehydrate. Its structure, in common with other catecholamines, is that of a benzene ring with hydroxyl group substituted at positions 3 and 4, and an ethalyamine side chain.

It is believed that β -adrenergic effects result from stimulation of the production of cyclic adenosine-3',5'-monophosphate (AMP) by activation of the enzyme adenyl cyclase. The main effects of therapeutic doses of isoproterenol are relaxation of smooth muscle of the bronchial tree, cardiac stimulation, and peripheral vasodilation.

Isoprenaline induced peripheral vasodilation leads to a fall in systemic vascular resistance and a drop in diastolic blood pressure. Mean arterial pressure typically drops although systolic pressure is supported by myocardial inotropic and chronotropic responses facilitating an increased cardiac output. Myocardial Oxygen demand rises which may lead to ischaemia if in conjunction with obstructive coronary disease.

Cardiac effects can include sinus tachycardia, palpitations and arrhythmia. Flushing sensations are common, side effects can also include headaches. Isoprenaline is not known to cause QT prolongation.

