Part B of the project investigates the ability versus placebo of an isoprenaline infusion to induce atrial fibrillation and also any change in that inducibility associated with different ablation procedures. Subjects will be recruited based on their medical history and need for an ablation procedure. Subjects will be randomised in a double blinded fashion to receive isoprenaline or placebo infusions. The study drug infusion that they are randomised to will be delivered before and after their clinically indicated ablation procedure in the cardiac catheter laboratory environment whilst the subject is under sedation for that procedure. There will be follow up requirements for study subjects over and above the standard clinical follow up procedure.

Endpoints

Study Endpoints

Experiments 1, 5 and 6

Primary Endpoint

• Change in outcome between two administrations of the study drug infusion protocol **Secondary Endpoints**

- Change in time to outcome between two administrations of the study drug infusion protocol
- Change in maximum rate of infusion between two administrations of the study drug infusion protocol

Experiments 2, 3 and 4

Primary Endpoints

- Frequency of the occurrence of atrial fibrillation lasting greater than 30 seconds during study drug infusion protocol
- Frequency of the occurrence of an arrhythmia other than atrial fibrillation, sinus tachycardia or junctional rhythm lasting greater than 30 seconds during study drug infusion protocol

Secondary Endpoints

- Frequency of the occurrence of atrial fibrillation lasting less than 30 seconds during study drug infusion protocol
- Frequency of the occurrence of an arrhythmia other than atrial fibrillation, sinus tachycardia or junctional rhythm lasting less than 30 seconds during study drug infusion protocol
- Time from start of infusion protocol to occurrence of atrial fibrillation
- Rate of infusion at time of occurrence of atrial fibrillation
- Maximum tolerated rate of study drug infusion prior to its cessation for any reason

Infusion Endpoints

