Central to this project is the delivery of a standardised infusion protocol. This infusion will be an open label isoprenaline infusion in some parts of the project or will be a study drug infusion of either isoprenaline or placebo (normal saline) in other parts of the project. In all cases, each administration of an infusion will follow this protocol.

The infusion will be delivered to subjects in the supine position. Minimum monitoring of the participant at the time of the infusion will include non-invasive blood pressure monitoring at 1 minute intervals, continuous ECG monitoring, continuous monitoring of pulse oximetry and direct observation of the subject by a member of the study team. A blood sample to measure markers of response to the infusion may be taken during the infusion protocol, however such samples are an optional part of the consent process and do not constitute a core part of the study.

The study drug infusion will be drawn up in compliance with local policies regarding intravenous medications. Unblinded members of the nursing staff will identify whether the participant has been randomised to an isoprenaline infusion or to placebo. They will then draw up either 40 mls of normal saline (placebo infusion) into a 50 mls luer lock syringe or will make up the isoprenaline infusion in a 50 mls luer lock syringe. For the isoprenaline infusion, two ampules of isoprenaline sulphate, each containing 10 mls of 0.01 mg/ml solution will be added to 20 mls of normal saline. This will create 40 mls of 0.005mg/ml (5 micrograms/ml) solution containing a total of 0.2mg (200micrograms) isoprenaline sulphate.

The two infusions will be visually identical. The syringe will be labelled with the participant's candidate number, hospital number, name and date of birth but not with the syringe contents. All other cardiac electrophysiology laboratory staff and the study team will remain blinded. Unblinded nursing staff may attach and deliver the study drug infusion, however they should not be the nurse named to monitor the participant and they will not contribute to determination or recording of any study data. This process will only be required in the cardiac electrophysiology laboratory environment as all placebo controlled infusions will take place in this setting.

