- Occurrence of atrial fibrillation lasting greater than 30 seconds during study drug infusion protocol
- Occurrence of an arrhythmia other than atrial fibrillation, sinus tachycardia or junctional rhythm lasting greater than 30 seconds during study drug infusion protocol
- Discontinuation of the study drug infusion
 - Severe tremulousness or anxiety
 - Complaints of severe chest tightness
 - Decrease in systolic blood pressure to consistently < 70mmHg
 - Electrocardiographic changes suggestive of myocardial ischaemia

The diagnosis of atrial fibrillation will rest with the clinician acting as operator for the procedure aided by the attending cardiac physiologists.

If a subject experiences an arrhythmia lasting greater than 30 seconds and thus triggering the infusion to stop, they will be monitored for 10 minutes. It is anticipated from previous literature that in the majority of cases, subjects will have spontaneously reverted to normal sinus rhythm after this period of time. It is accepted however that in some cases an arrhythmia will persist beyond this point and in those cases, the supervising physician will restore sinus rhythm.

All subjects will be monitored for at least 30 minutes after an infusion administration.

At all infusions, the following data will be recorded

- Level of sedation at the start of the infusion (AVPU score)
- Total dose of sedation given in the 20 minutes prior to the start of the infusion

- The presence or absence of an episode of arrhythmia lasting greater than 30 seconds
 - The diagnosis for the arrhythmia seen
 - The time from initiation of the infusion to the start of the episode of arrhythmia lasting greater than 30 seconds
 - The time from the start of the episode of arrhythmia lasting greater than 30 seconds to the restoration of sinus rhythm
 - The method of restoration of sinus rhythm
- The presence or absence of one of the other reasons for stopping the infusion
 - The reason for stopping the infusion
- The time from the start of the infusion to its cessation for whatever reason
- The maximum rate of infusion delivered to the study subject
- Minute by minute heart rate and blood pressure measurements over the course of the infusion
- The presence of episodes of arrhythmia lasting less than 30 seconds
 - The diagnosis for each arrhythmia seen
 - The time from initiation of the infusion to the start of each episode of arrhythmia lasting less than 30 seconds

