It is noted that this study runs alongside standard NHS care for many participants which includes a cardiac catheter ablation procedure. It is anticipated from registry data regarding the rate of complication(53)(54) associated with such procedures will mean that some participants will experience them. Below is a list of serious adverse events which may occur during the study but

which the investigators would expect that, upon full review, would be linked with the ablation procedure, rather than the administration of the study drug protocol.

- Cardiac Tamponade or Perforation
- Vascular Access Complication
- Haematoma
- Pulmonary Vein Stenosis
- Atrio-Oesophageal Fistula formation

Un-blinding Procedure

If, in the context of a medical emergency, the clinical team caring for the participant require unblinding as to the contents of the study drug infusion, this will occur immediately. The most simple method for this to occur is that the un-blinded nurse who drew up the study drug can be asked directly to inform the clinical team and / or investigators as to the contents of the infusion. It is anticipated that the nurse will remain be in the room for the duration of the infusion in all cases but will not take part in any of the subsequent study procedures or observations.

If the nurse is unsure as to the contents of the infusion for any reason, or if the nurse who drew up the study infusion is not present for any reason, the participant's study number can be correlated with the instructions in the randomisation folder from which the un-blinded nurses will determine which infusion to draw up. This document will be kept within the cardiac electrophysiology laboratory and so will be available immediately.

Un-blinding will always be reported as a serious adverse event.

Reporting procedure

All adverse events should be reported. Depending on the nature of the event the reporting procedures below should be followed. Any questions concerning adverse event reporting should be directed to the Chief Investigator in the first instance. All project team members will be GCP trained.

All such events, whether expected or not, should be recorded in the CRF. In the event of an adverse event/reaction, a member of research team will:

- Review all documentation (e.g. hospital notes, laboratory and diagnostic reports) relevant to the event
- Record the event and relevant comments in the subject's medical notes (or source data where this is not the medical notes)

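### Part B is called double blind, but masking rests on the look of the syringe, and the operator who decides the AF endpoint is likely to be able to infer the arm from the drug response

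*Protocol*

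**What the plan says.** Under Study Design, Part B is described in these terms: "Subjects will be randomised in a double blinded fashion to receive isoprenaline or placebo infusions". The first primary endpoint of Experiments 2 to 4 is "Frequency of the occurrence of atrial fibrillation lasting greater than 30 seconds during study drug infusion protocol"; the second is the corresponding count for other arrhythmias.

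The masking measures are in the Infusion Protocol section. The comparator is normal saline, "The two infusions will be visually identical", and the syringe does not carry its contents. Unblinded nurses prepare the infusion, and "they will not contribute to determination or recording of any study data". For everyone else the statement is "All other cardiac electrophysiology laboratory staff and the study team will remain blinded".

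The same section assigns the endpoint decision: "The diagnosis of atrial fibrillation will rest with the clinician acting as operator for the procedure aided by the attending cardiac physiologists". That decision also stops the infusion. Part B, Visit 2 has the operator attach the infusion, with heart rate and blood pressure taken at one-minute intervals, and the infusion is given before and after ablation.

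On pharmacology, the IMP section says "Cardiac effects can include sinus tachycardia, palpitations and arrhythmia", and the adverse event table lists tachycardia, hypotension, flushing and mild tremor as common.

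On the randomisation folder, the Un-blinding Procedure section says "This document will be kept within the cardiac electrophysiology laboratory and so will be available immediately".

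**The concern.** An identical-looking syringe masks the preparation, not the response. A beta-agonist stepped up to 25 mcg/min is compared with a fluid that has no such action, and the people who judge the endpoint must watch the ECG to do so. The protocol's statement that they stay masked is therefore one that the design is unlikely to deliver for the endpoint assessor.

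Both primary endpoints of Experiments 2 to 4 depend on live judgement at two margins: AF against another arrhythmia, and just under against just over 30 seconds. If calls at those margins are influenced by a guess at the arm, the error differs between arms and randomisation does not remove it. The point matters more here than in most trials, because the protocol's own case for the study is that earlier work lacked a proper control.

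**Working it through.** **1. What the assessor can see**

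| Feature | Protocol section | Bearing on masking |
|---|---|---|
| Visually identical, unlabelled syringes | Infusion Protocol | Masks the preparation |
| Isoprenaline 5 to 25 mcg/min v saline | Infusion Protocol | Heart-rate response expected in one arm only |
| Continuous ECG, blood pressure every minute, direct observation | Infusion Protocol | The response is on display |
| Operator attaches the infusion and decides on AF | Part B, Visit 2; Infusion Protocol | The assessor is present throughout |
| Physiologists aid the diagnosis | Infusion Protocol | They see the same monitors |
| Same allocation before and after ablation | Study Procedure, Part B | The response is usually seen twice |

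Participants in persistent arrhythmia at the start skip the first infusion, hence *usually*. Part A is open label by design and is not affected.

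**2. The plan's own figure**

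Inputs (Sample Size Calculation): 1% v 30%, two-sided 5%, 90% power. With pooled variance, mean rate 0.155:

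n = [1.960·√(2·0.155·0.845) + 1.282·√(0.01·0.99 + 0.30·0.70)]² / 0.29² = (1.003 + 0.601)² / 0.0841 = 30.6, so 31 per arm. This agrees with the protocol. The point does not concern the sample size.

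**3. What differential calling could do**

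The documents give no misclassification rate, so f is an assumption: the share of AF-free isoprenaline recipients wrongly called AF, with saline calls correct. The observed isoprenaline rate is p + (1 − p)·f. Rejection rates come from exact enumeration of two binomials at 30 per arm (the Experiment 2 target). Fisher's two-sided test at 5% is used, since the protocol names it for small counts.

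| True rates | f | Observed isoprenaline rate | Chance of significance |
|---|---|---|---|
| 1% v 1% | 0 | 1.0% | about 0% |
| | 5% | 0.01 + 0.99·0.05 = 6.0% | 0.6% |
| | 10% | 0.01 + 0.99·0.10 = 10.9% | 8% |
| 30% v 1% | 0 | 30.0% | 86% |
| | 5% | 0.30 + 0.70·0.05 = 33.5% | 93% |
| | 10% | 0.30 + 0.70·0.10 = 37.0% | 96% |

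The uncorrected chi-squared test is more sensitive: with 1% v 1% it gives about 0, 7.6 and 33% for the same three values of f. At 35 per arm (Experiments 3 and 4), Fisher's test gives about 0, 1.2 and 13%.

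**4. The opposite direction**

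If instead a share g of true isoprenaline AF episodes is missed, the observed rate is 0.30·(1 − g). For g = 5 and 10% this is 28.5 and 27.0%, and Fisher power at 30 per arm against 1% falls from 86% to 83% and 78%.

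**The case against.** The strongest reply is that no inert placebo can hide a rise in heart rate, so operator unmasking comes with the comparison, and that AF lasting over 30 seconds on continuous ECG is a fairly objective endpoint with recorded episode timings. Both points stand. They limit the bias to borderline calls. They do not support saying that these staff stay masked, and they do not explain why the endpoint is left to the live call when a recording could be read later.

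Four stronger readings are tempting, and the documents do not support them:

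- *The operator alone makes the diagnosis.* The protocol says that physiologists aid it. They see the same monitors, so this corrects the description without curing the problem.
- *The operator can tell the arm.* This is an inference from stated pharmacology, however strong. The text supports only that the operator is likely to be able to infer it.
- *The bias favours isoprenaline.* The Sample Size Calculation section records that the published rate above 80% does not match the investigators' own experience, so their stated prior is sceptical. Operators' expectations are not given, and under-calling is as arguable as over-calling.
- *The folder exposes future allocations.* The protocol describes it as the preparing nurses' document and a back-up for emergency unblinding. Nothing says that operators may consult it. What can be said is that it sits in the blinded staff's workplace and that no access control is stated.

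**Conclusion.** The point holds in limited form. The double-blind description is unlikely to be true of the endpoint assessor in Part B, and the protocol describes no masked reading that would make up for it. This rests on the protocol's own account of the drug, the monitoring and who decides.

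The size of any bias is unknown. On the assumed range above, false positives under no drug effect stay near zero with Fisher's test at 5% over-calling and reach 8% at 10%. At the planned effect the conclusion would seldom change. The exposure is therefore greatest where the true effect is small or absent. A reader might infer that a positive result could not be trusted; the figures do not support that for an effect of the planned size. The sample size need not change.

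**What to change.** 1. **Describe the masking as it is.** State that the participant and the syringe are masked and that the operator and attending physiologists are probably unmasked by drug effect. Remove the statement that these staff stay blinded.
2. **Separate the live call from the endpoint.** Leave the operator's live call in place for stopping the infusion. Save the full ECG of every infusion in both arms, not only strips that the operator selects, so that missed episodes can also be found. Take the AF and 30-second endpoints from that recording against fixed criteria. Have it read under code by an existing study-team member who was not in the room, with arm and heart-rate trend withheld as far as possible. State in advance how a live call that is later reversed is counted, because the infusion will already have been stopped.
3. **Control access to allocations.** Replace the folder with one sealed, opaque, numbered envelope per participant, opened only by the preparing nurse or for emergency unblinding. It can stay in the laboratory, so emergency access remains immediate.

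The cost is protocol wording, envelopes, and some storage and reading time. The protocol requires continuous ECG monitoring but does not say that recordings are kept, so storage is a real though modest addition. No extra reader or panel is needed. The drawbacks are a less favourable description of masking, and that heart rate within the tracing may still hint at the arm.
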